- Rationale for afatinib or other systemic therapy discontinuation

AEs will be collected and analyzed in the Clinical Study Report. Providers will be shown information describing what constitutes an AE/ADR/SAE/FAE per BI policies. The processes for safety reporting and analysis of the safety data will be implemented and conducted as per the BI non-interventional study (NIS) standard operating procedures. [REDACTED] will complete any reporting of events to BI per event reporting protocols.

The diagnosis, time, attribution (treatment-related or not per provider interpretation) and severity of the reported AEs during index therapy will be collected. If death is cited as rationale for discontinuation then provider will abstract data related to date of death, cause of death.

Table 3. Adverse events data collection.

Variable	Definition / response options
AEs during a given line of therapy	During each line of therapy, providers will indicate the AE that occurred including severity.
Start date of AE	Date each AE occurred

Severity (see section 11.1)	
Severity of each AE, as assessed by the provider, provided the following guidance:
 
 • Mild (mild symptoms; clinical or diagnostic observations only [e.g. lab work]; intervention not performed) • Moderate (minimal, local or noninvasive intervention performed [e.g., administration of fluids]) • Severe (medically significant ranging from not immediately life-threatening, life-threatening consequences, to death related to AE; [e.g., extensive monitoring, hospitalization or prolongation of hospitalization])
Resolution	
Outcome of each AE will be collected as:
 
 • Recovered/Resolved • Recovered/Resolved with sequelae • Not yet recovered/Not yet resolved • Fatal • Unknown
Outcome	
For all AEs, the outcome of the AE, regardless of severity indicated, will be assessed by participating providers. These outcomes will allow for the classification of serious and fatal AEs as defined in Section 11
 
 • Dose reduction • Dose hold/dose delay/schedule change • Discontinuation of treatment • Unscheduled office visit/treatment • Resulting in death • Life-threatening • Required inpatient hospitalization • Resulted in persistent or significant disability • Prolonged existing hospitalization
End date of AE	Date AE resolved/patient recovered (if resolved/recovered)

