11.1 DEFINITIONS OF ADVERSE EVENTS

Adverse event (AE)

AE is defined as any untoward medical occurrence in a patient or clinical investigation subject administered a medicinal product and which does not necessarily have a causal relationship with this treatment.

An AE can therefore be any unfavourable and unintended sign (e.g., abnormal laboratory finding), symptom, or disease temporally associated with the use of a medicinal product, whether considered related to the medicinal product.

Adverse drug reaction (ADR)

An ADR is defined as a response to a medicinal product which is noxious and unintended. Response in this context means that a causal relationship between a medicinal product and an AE is at least a reasonable possibility. Adverse reactions may arise from the use of the product within or outside the terms of the marketing authorization or from occupational exposure. Conditions of use outside the marketing authorization include off-label use, overdose, misuse, abuse, and medication errors.

Serious adverse event (SAE)

SAE is defined as any AE that:

- results in death
- is life-threatening
- requires in-patient hospitalization, or
- prolongation of existing hospitalization
- results in persistent or significant disability or incapacity, or
- is a congenital anomaly/birth defect

Life-threatening in this context refers to an event in which the patient was at risk of death at the time of the event; it does not refer to an event that hypothetically might have caused death if more severe.

Medical and scientific judgment should be exercised in deciding whether other situations should be considered serious events, such as important medical events that might not be immediately life-threatening or result in death or hospitalization but may jeopardize the patient or might require intervention to prevent one of the other outcomes listed above.

Examples of such events are intensive treatment in an emergency room or at home for allergic bronchospasm, blood dyscrasias, or convulsions that do not result in hospitalization or development of drug dependency or drug abuse. Any suspected transmission via a medicinal product of an infectious agent is also considered a serious adverse reaction.

No AESIs have been defined for this study.

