- Continuation of the event despite the withdrawal of the medication, considering the pharmacological properties of the compound (e.g., after five half-lives). Of note, this criterion may not apply to events whose time course is prolonged despite removing the original trigger.
- Additional arguments amongst those stated before, like alternative explanation (e.g., situations where other drugs or underlying diseases appear to provide a more likely explanation for the observed event than the drug concerned).
- Disappearance of the event even though the study drug treatment continues or remains unchanged.

Intensity of AE

Providers will be asked to classify AEs as mild, moderate, or severe based on the medical intervention associated with the AE (see below).

- Mild: mild symptoms; clinical or diagnostic observations only (e.g., lab work); intervention not performed
- Moderate: minimal, local, or noninvasive intervention performed (e.g., administration of fluids)
- Severe: medically significant, ranging from not immediately life-threatening, life-threatening consequences, to death related to AE; (e.g., extensive monitoring, hospitalization or prolongation of hospitalization)

Regardless of the severity of the AE indicated by the provider, the following outcomes will be collected for all AEs, in order to further classify them as serious and/or fatal.

- Resulting in death
- Life-threatening
- Required inpatient hospitalization
- Resulted in persistent or significant disability
- Prolonged existing hospitalization

Pregnancy

In rare cases, pregnancy might have occurred during the study period. Patients who were identified as pregnant while on afatinib will be reviewed. Any drug exposure during pregnancy, which occurred in a female patient or a partner to a male patient will be reported by means of Part A of the Pregnancy Monitoring Form. The outcome of the pregnancy associated with drug exposure during pregnancy must be followed up and reported by means of Part B of the Pregnancy Monitoring Form.

In the absence of a reportable AE, only the Pregnancy Monitoring Form must be completed. Otherwise, the NIS AE form is to be completed and forwarded as well within the respective timelines.

Expedited reporting of AEs and drug exposure during pregnancy

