The following must be reported by the investigator on the NIS AE form and/or Pregnancy Monitoring Form from start of data extraction once informed consent is signed (if required) onwards until the end of data extraction and provide to BI unique entry point:

Type of Report	Timeline
All serious ADRs associated with afatinib	immediately within 24 hours
All AEs with fatal outcome in patients exposed to afatinib *Exemption applies	immediately within 24 hours
All non-serious ADRs associated with afatinib	7 calendar days
Drug exposure during pregnancy	7 calendar days

The same timelines apply if follow-up information becomes available for the respective events. In specific occasions, the Investigator could inform the Sponsor upfront via telephone. This does not replace the requirement to complete and fax and/or email the NIS AE Form.

*Exemption

Death due to disease progression of the underlying malignancy is a study endpoint and the natural course of the disease. As such, it is exempted from reporting as an SAE. Progression of the subject's underlying malignancy will be recorded on the appropriate pages of the eCRF only and will not be reported on the NIS AE Form. However, when there is evidence suggesting a causal relationship between afatinib and the progression of the underlying malignancy, the event must be reported as an SAE on the NIS AE Form and on the eCRF.

Information required

For each reportable AE, the investigator should provide the information requested on the appropriate CRF pages and the NIS AE form.

Reporting of AEs assessed as related to any other BI drug

The investigator is encouraged to report all AEs related to any BI drug other than afatinib according to the local regulatory requirements for spontaneous AE reporting at the investigator's discretion by using the locally established routes and AE report forms. The term AE includes drug exposure during pregnancy, and, regardless of whether an AE occurred or not, any abuse, off-label use, misuse, medication error, occupational exposure, lack of effect, and unexpected benefit.

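### The outcome boxes meant to classify serious AEs cover less than the protocol's own SAE definition, chiefly by leaving out important medical events

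*Combined protocol and SAP*

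**What the plan says.** Section 9.3.2, Table 3, has providers record outcomes for every AE whatever its severity, and gives the reason: "These outcomes will allow for the classification of serious and fatal AEs as defined in Section 11". Nine boxes follow. Section 11.2.1, under the intensity of AEs, repeats the purpose ("the following outcomes will be collected for all AEs, in order to further classify them as serious and/or fatal") and lists five of those nine.

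Section 11.1 gives the definition that Table 3 relies on. Its sixth listed criterion is that the event "is a congenital anomaly/birth defect". It then asks for medical and scientific judgment on other situations, "such as important medical events that might not be immediately life-threatening or result in death or hospitalization", where the event may endanger the patient or need intervention to prevent a listed outcome. It illustrates the clause: "Examples of such events are intensive treatment in an emergency room or at home for allergic bronchospasm, blood dyscrasias, or convulsions", in cases that do not lead to admission.

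Two other provisions bear on the point. Section 9.3.2 says "Providers will be shown information describing what constitutes an AE/ADR/SAE/FAE per BI policies". Section 11.2.1 sets an expedited route on the NIS AE form, with 24 hours for "All serious ADRs associated with afatinib" and 7 calendar days for non-serious ADRs to afatinib.

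**The concern.** A set of boxes can classify events by a definition only if each criterion can be recorded. Here an event that is serious solely because it is medically important, such as a convulsion treated in an emergency room without admission, can be entered as an AE, but no field shows that it was serious. Anyone deriving a seriousness flag from the eCRF would have nothing to derive it from.

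What is at stake is the meaning of any serious AE figure taken from this dataset. Sections 4 and 7 say the data may support label-expansion applications, and a reader would assume that serious has the Section 11.1 meaning. The gap would also be hard to close later. Section 9.4.1 says no source documents are provided for verification, and the random validation in Section 9.8.2 re-enters three data points, with index treatment dates and stage as examples.

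**Working it through.** There is no planned figure to reproduce. The check sets the definition against the fields, item by item.

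| Ground for seriousness in 11.1 | Box in Table 3 | In the 11.2.1 list |
|---|---|---|
| Death | yes | yes |
| Life-threatening | yes | yes |
| Inpatient hospitalization | yes | yes |
| Prolonged hospitalization | yes | yes |
| Persistent or significant disability | yes | yes |
| Congenital anomaly or birth defect | no | no |
| Important medical event, by judgment | no | no |

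Coverage is 5 of 7 in both places. (Section 11.1 also treats suspected transmission of an infectious agent through a medicinal product as a serious reaction. It has no box either; I have not counted it separately.) The fatal half of the promise is met, because death has an outcome box and is also a category under Resolution. The shortfall is in the serious half only.

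Could another field fill the gap?

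- The other four of the nine Table 3 boxes are dose reduction, dose hold or delay, treatment discontinuation, and "Unscheduled office visit/treatment". The last might be ticked for emergency-room care, but it is not a seriousness criterion in 11.1 and is absent from the 11.2.1 list.
- The Severe grade mentions medical significance, but the plan collects these outcomes regardless of severity, so the grade cannot stand in for seriousness.
- The free-text option in Table 2 concerns the AE term.
- The Pregnancy Monitoring Form, Part B, follows the outcome of exposed pregnancies, so it largely covers congenital anomaly.
- The expedited table in 11.2.1 covers ADRs to afatinib, fatal AEs in afatinib-exposed patients, and exposure during pregnancy. That leaves no route for non-fatal unrelated AEs in afatinib patients, or for non-fatal AEs in the other-therapy cohort. No reconciliation of the NIS AE form with the eCRF is described.

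For scale only, suppose a share q of patients has at least one event that is serious solely on a missing ground. The documents give no value for q, so 1% to 10% is an assumption.

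- Expected patients affected, n × q: 0.7 to 7.0 of 70 on afatinib, 0.5 to 5.0 of 50 on other therapy, 1.2 to 12.0 of 120 in all.
- Chance of at least one among 120, 1 − (1 − q)^120: 1 − 0.99^120 = 70% at q = 1%, and 1 − 0.97^120 = 97% at q = 3%.

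This shows that even a low rate would probably produce a case. It does not estimate the rate.

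**The case against.** The strongest reply is that no planned output changes. Objective 5 and Section 9.7 call for incidence, severity and timing of AEs; seriousness is not named as something to tabulate. All AEs are collected whether serious or not, and a medically important event may still appear in the severity summary. Section 9.9 already concedes under-reporting and says AE frequency cannot be confirmed from this dataset. Nor does the plan say that an AE with no box ticked is non-serious. Table 3 defers to Section 11, which calls for judgment, and providers are shown what counts as an SAE.

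Most of this stands as a limit on the consequences. A reader might infer that the report's SAE tables will understate SAE incidence in both cohorts, but the documents do not support that as stated, because no such table is specified. A reader might also infer that a serious afatinib reaction would slip from the 24-hour to the 7-day route. That is not shown either: expedited reporting is a separate investigator duty on the NIS AE form, the 11.1 definition applies to it, and nothing says the eCRF boxes drive it.

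What the reply does not remove is the promise itself. The plan says these fields support classification under Section 11. Showing providers a definition does not help if there is nowhere to record the resulting judgment.

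**Conclusion.** The point holds as an inconsistency between what the eCRF outcome list is said to do and what it can do. Its practical weight lies with important medical events; congenital anomaly matters little in adults treated for solid tumors. The gap is clearest for non-fatal AEs in the other-therapy cohort and non-fatal unrelated AEs in afatinib patients, for which the documents offer no second source on seriousness.

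The number of events affected cannot be derived from the documents, and they establish neither a biased planned table nor a delayed report. The conclusion assumes that the eCRF carries the boxes as Table 3 lists them, and that any serious AE classification would be taken from those fields. It is worth correcting because the change is small and the missing information would be hard to recover after abstraction.

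**What to change.** Add two items to the outcome list in Table 3, in Section 11.2.1 and in the eCRF: other medically important event (per 11.1), and congenital anomaly or birth defect. State that an AE is flagged as serious if any of the resulting seven seriousness boxes is ticked, and that the four boxes on dose changes, discontinuation and unscheduled visits do not count towards the flag. Coverage of the definition then goes from 5 of 7 to 7 of 7.

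If the sponsor prefers not to change the form, the minimum is to correct the sentence in Table 3 and its counterpart in 11.2.1 to say that the eCRF classification is narrower than Section 11.1, and to repeat this wherever a serious AE count is reported.

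The cost is two boxes and slightly more provider judgment per AE. It is best done before the pre-test, since Section 9.8.1 requires the eCRF and protocol to go back to the IRB for changes arising from it.

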9.3.3 Covariates

Patient demographics clinical characteristics will be described in each cohort of patients. As described above, these variables will be summarized descriptively as study outcomes and also

considered as covariates to contextualize the clinical outcomes of the study (e.g., ORR, DOR, PFS, TOT, OS, AEs). These variables are described in Section **9.3.2 Outcomes**, above.

9.4 DATA SOURCES

All study data will be entered by the investigators into the eCRF. The eCRF captures data for each of the study variables described in **Section 9.3 - Variables**. The eCRF is designed to allow providers to efficiently move through the patient chart or EMR based on the journey of the patient through the course of disease. The eCRF conforms to the rules and regulations of the Health Insurance Portability and Accountability Act (HIPAA) of 1996 governing the abstraction and storage of protected health information (PHI).

De-identified, patient-level data will be obtained from providers in the [REDACTED] [REDACTED] who will complete an electronic case report form (eCRF) for eligible patients. [REDACTED]

[REDACTED] will recruit providers from [REDACTED] to participate. [REDACTED] is a community of over 7,000 oncologists, hematologists and urologists from across the U.S., with varying levels of time in practice, from practices both within and outside of group purchasing organizations. A subset of this group (~800) participates in retrospective observational research studies. All provider participation in the study is voluntary.

To be eligible to participate, providers must have treated at least one patient meeting the study eligibility criteria, be able to participate in research approved by an external institutional review board (IRB), and agree to participate in data quality control processes. No provider at practices that require local IRB approval at the practice will be eligible to participate. A waiver of obtaining patient consent will be sought for the study. No protected health information (PHI) beyond dates of diagnosis, treatments, and outcomes will be collected.

Providers will abstract demographic-, clinical-, and treatment- related data as available from the patient's electronic health record (EHR), starting from the time of primary malignancy diagnosis through the last date of follow-up with the patient or death. Providers will complete an eCRF for all eligible patients and will begin data abstraction beginning with the first eligible patients and select consecutive patients moving forward in time. Data elements that are required are specified in the study inclusion/exclusion criteria; non-required data elements may be missing/unknown. Providers may abstract data into the eCRF for both patients they personally managed/treated or those managed/treated by other providers within their practice.

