9.2 SETTING

Approximately 20 or more unique providers will participate in this research study. To minimize potential bias, the maximum number of patients each provider may select and complete data abstraction for is capped at 30; for any provider who submits >10 patients, their data will be reviewed in detail by a clinician and analyst to identify any data quality issues (see Section **9.8.2 Data Validation** for further details on data quality assurance and control measures). Data

will be collected through an electronic case report form (eCRF) completed by the patients' providers who volunteer to participate in the study. Providers will be compensated at fair market value for the time to complete data abstraction and quality control procedures, which are estimated to take up to 1 hour per patient.

Recruitment of providers will be conducted electronically. Providers who responded to an initial feasibility request and reported treating potentially eligible patients will be contacted and invited to participate. Recruitment to fill the up-to-120-patient quota will run for 4 weeks from the date of recruitment launch. During that time, the per-cohort quotas will be electronically monitored to ensure that the final number of patients achieves up to 70 patients with *NRG1* gene fusion-positive solid tumors treated with afatinib and up to 50 with an *NRG1* gene fusion-positive solid tumor not treated with afatinib at the time of data collection. As recruitment for a cohort is completed, no further patient data entry will be allowed for that cohort; however, providers actively completing an eCRF at the time of quota close for a cohort will be allowed to complete that eCRF, and the total number of patients per cohort may exceed the quotas.

Providers will be asked to identify all eligible patients, and starting with the earliest index date, chronologically select consecutive patients meeting the eligibility criteria and complete the data abstraction. The eCRF is structured to allow data collection regarding patient clinical history at the time of initial diagnosis of their solid tumor, initiation of index therapy (including dates of dose starts, stops, and interruptions), response to therapy, dates of disease progression, AEs, (including dates of onset, recovery, and reported deaths).

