9.4.1 Source Documents

Providers are compensated for their time completing data abstraction into the eCRF and subsequent data verification as necessary. No source documents will be provided to [REDACTED] for verification; however, [REDACTED] will require duplicate data entry for a sample of patients (see **Section 9.8.2 Data Validation**) after initial data collection to verify data point accuracy.

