9.4.2 Dataset and Records

9.5 STUDY SIZE

The total target number of patients is up to 120 patients, including up to 70 patients with an *NRG1* gene fusion-positive solid tumor treated with afatinib and up to 50 patients with an *NRG1* gene fusion-positive solid tumor who had not received afatinib at the time of data collection. The target number of patients was based on the results of a pilot feasibility study conducted by [REDACTED] with BI.

In December 2019, [REDACTED] conducted outreach to approximately 800 providers in [REDACTED] to inquire as to the number of patients with *NRG1* gene fusion-positive solid tumors treated with afatinib they had personally managed or who were cared for at their practice. Providers were presented with similar inclusion criteria as those described herein. In total, 12 oncologists completed short eCRFs describing a total of 108 patients. Of the 108, 67 patients were treated with afatinib and 41 had not received afatinib therapy.

Based on the feasibility study, [REDACTED] will target number of patients of up to 70 afatinib-treated patients with *NRG1* gene fusion-positive solid tumors and up to 50 patients with *NRG1* gene fusion-positive solid tumors who have not received afatinib. Although the feasibility study did not identify this number of patients, further recruitment to non-responders to the survey invitation will be used to achieve the target number of patients planned for this study. Given the small number of patients targeted for study inclusion and anticipated differences in baseline characteristics between afatinib-treated and patients treated with other systemic therapies, statistical comparisons are not planned. In lieu of a comparative analysis between the afatinib-treated and non-afatinib treated patients are exploratory, the number of patients in each cohort and the precision of estimates are presented (**Table 4**). With up to 70 patients in the afatinib-treated cohort, the standard error (SE) of any bivariate response variable is expected to be between 5.5% and 11.7%.

Table 4. Precision of point estimates around number of patients.

Point Estimate of Proportion	Total Number of eCRFs				
	n=30 (SE)	n=50 (SE)	n=70 (SE)	n=100 (SE)	n=150 (SE)
5%	± 7.8%	± 6.0%	± 5.5%	± 4.3%	± 3.6%
20%	± 14.3%	± 11.1%	± 9.4%	± 7.8%	± 6.4%
30%	± 16.4%	± 12.7%	± 10.7%	± 9.0%	± 7.3%
40%	± 17.5%	± 13.6%	± 11.5%	± 9.6%	± 7.8%
50%	± 17.9%	± 13.9%	± 11.7%	± 9.8%	± 8.0%

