9.8.2 Data Validation

Multiple levels of quality control and quality assessment occur during the study. First, the eCRF includes programmed internal validity checks, including date validation (e.g., date of initiation of index therapy cannot occur before date of initial diagnosis of cancer) and logic that forces providers to respond to required questions. Next, the eCRF will be pre-tested with four clinicians prior to data collection. During this pre-test, [REDACTED] staff will hold a web-based conference with a selected provider during which the provider will abstract data into the eCRF while [REDACTED] research staff members monitor and probe the provider regarding the clarity of eCRF data fields. After conducting this pre-test, [REDACTED] will present findings to BI and suggest revisions to the eCRF as needed. The revised eCRF will be filed with the study IRB.

During data collection, [REDACTED] clinical research staff review all submitted eCRFs inspecting each for implausible patient clinical profiles based on treatment sequencing, lab and radiology results, or outcomes that are inconsistent with known clinical parameters, or other clinical data that are inconsistent with known standards and outcomes. In addition to review of the submitted data by the clinical research team, the study statistician will conduct an analysis of submitted data to identify any data points inconsistent (outliers) with the study population average. This analysis will include a descriptive analysis of the provider characteristics, demographics, baseline clinical and disease characteristics, and characteristics of treatment patterns (e.g., TOT). Data points flagged as outliers will be delivered to the clinical research team for further assessment.

Should outliers be discovered, [REDACTED] clinical research would contact the provider submitting the eCRF for data validation. All providers are informed in their contractual agreement that

follow-up with clinical staff at [REDACTED] may be required. Participating providers are asked to create a 4-digit unique identifier code per patient that is provided to [REDACTED] through the eCRF and used for identifying the patient record for validation between [REDACTED] and the provider. Individual eCRFs will be removed from providers unable to validate a data point, and resampling will not occur. All other data will be considered valid provided additional patients from that provider are not selected for random validation.

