10 PROTECTION OF HUMAN SUBJECTS

Individual patient medical information obtained as a result of this study is considered confidential and disclosure to third parties is prohibited. All study materials including the research protocol and paper-version of the eCRF will be reviewed by a central IRB prior to any data abstraction including field-testing of the eCRF. A waiver of HIPAA authorization for use of PHI will be requested from the IRB since the following three requirements will be met:

1. The use or disclosure of the PHI involves no more than minimal risk to the individuals, based on the following elements:
 - a. An adequate plan to protect identifiers from improper use and disclosure;
 - b. An adequate plan to destroy the identifiers at the earliest opportunity consistent with conduct of the research (unless there is a health or research justification for retaining the identifiers, or such retention is otherwise required by law); and
 - c. Adequate written assurances that the PHI will not be reused or redislosed to any other person or entity, except as required by law, for authorized oversight of the research project, or for other research for which the use or disclosure of PHI would be permitted by HIPAA.
2. The research could not be practicably conducted without access to and use of the PHI; and
3. The research could not practicably be conducted without the waiver.

Providers are required to be able to participate in research covered by a central IRB. At all times, patients' PHI will be kept confidential in accordance with HIPAA. The eCRF will not capture any data related to the patient's name, full date of birth, social security number, health insurance plan number, medical record number, or other such PHI. However, date of disease diagnosis, date(s) of treatment(s) administered (including dates of dose changes), date of the development of health states of interest (i.e., SAEs/FAEs, disease progression), and date of death (if available) will be collected in the eCRF. These items are considered PHI under HIPAA. All study results will be reported in aggregate; however, an anonymized patient-level dataset will be delivered to BI at the completion of the analytic cohort build.

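### Providers may enter colleagues' patients under codes they create themselves, and no stated check compares records between providers, so a patient entered twice would not be looked for

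*Combined protocol and SAP*

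**What the plan says.** Recruitment is by individual provider. Section 9.2 states: "Approximately 20 or more unique providers will participate in this research study". No limit of one provider per practice is stated. The cap of 30 patients, and the detailed review of anyone submitting more than 10, apply per provider.

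Section 9.4 lets a provider go beyond their own caseload: "Providers may abstract data into the eCRF for both patients they personally managed/treated or those managed/treated by other providers within their practice". Sections 9.2 and 9.12 ask each provider to begin with the earliest eligible index date and proceed consecutively.

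On identification, Section 9.8.2 says: "Participating providers are asked to create a 4-digit unique identifier code per patient". The code's stated use is to let the research vendor and that provider find the record again for validation. Section 10 adds: "The eCRF will not capture any data related to the patient's name, full date of birth, social security number"; record numbers are also excluded. Dates of diagnosis, treatment, progression and death are collected. Under Section 9.4.1 the vendor receives no source documents.

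Section 9.2 monitors the quotas of up to 70 and up to 50 patients electronically and closes each to further data entry once it is filled. The columns of Table 4 in Section 9.5 count eCRFs.

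**The concern.** Two colleagues in one practice who both follow these instructions would draw on the same pool of patients and begin at the same end of the list. Nothing tells them to divide it. The same patient would then arrive under two unrelated codes, and the analysis would treat the two records as two people.

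The certain consequences of a duplicate are an overstated count of unique patients and double weight for one patient's response, survival times and adverse events. Because quotas close on data entry, a duplicate can also take the place of a patient not yet entered. Intervals computed as if all records were independent would be too narrow. Sections 4 and 7 foresee use of these data in supplemental applications for label expansion, and there the number of distinct patients should be beyond question.

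**Working it through.** **Step 1. Would any stated check find a duplicate?**

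- Section 9.8.1 and the first paragraph of 9.8.2: programmed date, range and logic checks within a record. A genuine patient entered twice passes both times.
- Section 9.8.2, clinical review: each eCRF is inspected for implausible profiles. A real patient's profile is plausible.
- Section 9.8.2, statistical review: values far from the study average are flagged. A repeated record need not be an outlier.
- Section 9.8.2, random validation: one eCRF per provider, three data points re-entered by the same provider, with verified providers exempt. Each of two providers can re-enter the same patient correctly.
- Section 9.4.1, duplicate data entry: this is re-entry to test accuracy, not a search for repeated patients.
- Section 9.12, eligible patients compared with submitted patients: done within a provider.

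None of these compares one provider's records with another's.

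**Step 2. Reproduce the plan's figure.** Inputs from Table 4: n = 70, proportion 50%, stated precision ±11.7%. The column is labelled SE, but the value reproduces as a 95% half-width: 1.96 × √(0.25/70) = 11.71 points.

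**Step 3. Precision after duplicates are removed.** Let d be the number of patients entered twice among 70 records. The documents give no value, so d = 3, 6 and 10 are assumptions. Unique n = 70 − d, and the half-width at 50% is 1.96 × √(0.25/(70 − d)).

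**Step 4. If duplicates stay in.** Of the 70 records, 70 − 2d belong to patients entered once, and d patients have weight 2. The sum of squared weights is (70 − 2d) + 4d = 70 + 2d, so effective n = 70²/(70 + 2d). The analyst would still report 11.7. Approximate coverage of that nominal 95% interval is 2Φ(1.96 × √(effective n/70)) − 1.

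| d (assumed) | Unique n | Half-width at 50%, duplicates removed | Effective n, duplicates kept | Actual coverage |
|---|---|---|---|---|
| 0 | 70 | 11.7 | 70.0 | 95.0% |
| 3 | 67 | 12.0 | 4900/76 = 64.5 | 94.0% |
| 6 | 64 | 12.3 | 4900/82 = 59.8 | 93.0% |
| 10 | 60 | 12.7 | 4900/90 = 54.4 | 91.6% |

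**Step 5. ORR.** If being entered twice is unrelated to response, the expected ORR is unchanged. Bounds come from giving all duplicates the same response status. With an assumed 21 responses in 70 records (30.0%), removing d duplicates gives 21/(70 − d) if all are non-responders: 31.3%, 32.8% and 35.0% for d = 3, 6 and 10. If all are responders, (21 − d)/(70 − d) gives 26.9%, 23.4% and 18.3%. These are limits, not expectations.

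**The case against.** The strongest reply is that this is a possibility, not a demonstrated event. About 20 providers would come from a national community of over 7,000, some 800 of whom take part in such research, and two from one practice may never enrol. The documents give neither the number of providers per practice nor a duplicate rate. This stands, and it is why every count above is an assumption.

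The checks are also more than automated filters. Staff review all submitted eCRFs, a clinician and an analyst look in detail at larger contributors, and questionable records can be excluded. With about 120 records carrying fusion partner, test date and treatment dates, someone might notice a repeat. This also stands: what can be said is that no step is stated, not that a duplicate would certainly escape. In addition, Section 9.4.2 is a heading without text in this copy, and a record-handling rule could have stood there.

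A reader might infer three stronger things that the documents do not support:

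- **That ORR is distorted**, for instance because responders are remembered and entered more often. Selection is meant to be consecutive from the earliest index date, not by recall, so no link between duplication and response is given. The outer figures in Step 5 need every duplicate to share one response status.
- **That payment rewards duplicates.** Sections 9.2 and 9.4.1 describe compensation for time spent, and 9.8.2 withholds it for excluded data.
- **That the pilot count is inflated.** The 108 patients reported by 12 oncologists were those "they had personally managed or who were cared for at their practice", so overlap was possible there too. None is shown, and that count only set upper targets; it enters no estimate.

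The study is descriptive, with no hypothesis test and no comparison of cohorts, so a slightly narrow interval would reverse no formal conclusion.

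**Conclusion.** The gap is real but modest. A plan followed exactly could count one patient twice, provided that two participating providers share a practice, and no stated procedure compares records between providers. The effects that do not depend on response are an overstated number of unique patients, lost quota places and intervals that are somewhat too narrow. Under the assumed 3 to 10 duplicates in 70, the half-width at 50% after removal exceeds the Table 4 figure by 0.3 to 1.0 point (12.0 to 12.7 against 11.7). Leaving the duplicates in lowers coverage of a nominal 95% interval to between 94.0% and 91.6%. Bias in ORR is conditional on a relation between duplication and response for which the documents offer no evidence. This is a cheap improvement to the plan, not a flaw that invalidates it.

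**What to change.** In Section 9.8.2, record the practice of each participating provider. Before a record counts toward a cohort quota under Section 9.2, match it against all submitted records on sex, age, tumor type, fusion partner, NRG1 test date, and diagnosis and index dates. Table 1 and Section 10 show that these clinical fields and dates are already collected; only the practice field is new. Running the match across all records, not only within a practice, also covers patients who transfer care, which Section 9.9 anticipates.

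Resolve each match with the providers concerned, keep one record per patient, and report the number removed alongside the corrections and exclusions that Section 9.8.2 already undertakes to report.

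The cost is one added field, a short matching program for about 120 records, a few provider queries, and possibly a slightly smaller sample. Limiting each practice to one abstractor is not needed for this purpose. Combined with the cap of 30, it could shut out eligible patients at larger practices.
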